### 8.1.2. Relationship of Adverse Events to Study Drug

The Investigator's assessment of causality must be provided for all AEs (serious and non-serious). An Investigator's causality assessment is the determination of whether there exists a reasonable possibility that the investigational product caused or contributed to an AE.

- Not related: The AE is clearly not related to the study drug, or the temporal relationship of the onset of the AE relative to administration of the product is not reasonable, or the AE can

be explained by another cause such as an underlying medical condition or other concomitant medication, or the AE has no plausible relationship to study drug.

- Related: The AE is probably related to the study drug. The temporal relationship of the AE to administration of the product is reasonable and there is no other cause to explain the event. Adverse events should be classified as related if the Investigator feels there is evidence to suggest a causal relationship between the study drug and the AE.

Study drug related TEAEs will be summarized by SOC and PT for each treatment (active treatments, active treatment total, and pooled placebo) and overall.

### **8.1.3. Severity of Adverse Event**

All AEs will be assessed according to the National Cancer Institute (NCI) Common Terminology Criteria for Adverse Events (CTCAE), Version 5.

Table 1 will be used for assessing severity for AEs that are not specifically listed in the NCI CTCAE.

**Table 1: Adverse Event Severity Grading Scale for Events not Specifically Listed in NCI CTCAE**

Grade	Severity
1	Mild; asymptomatic or mild symptoms; clinical or diagnostic observations only; or intervention not indicated
2	Moderate; minimal, local, or non-invasive intervention indicated; or limiting age-appropriate instrumental activities of daily living [a]
3	Severe or medically significant, but not immediately life-threatening; hospitalization or prolongation of hospitalization indicated; disabling; or limiting self-care activities of daily living [b, c]
4	Life-threatening consequences or urgent intervention indicated [d]
5	Death related to adverse event [d]

- a. Instrumental activities of daily living refer to preparing meals, shopping for groceries or clothes, using the telephone, managing money, etc.
- b. Examples of self-care activities of daily living include bathing, dressing and undressing, feeding oneself, using the toilet, and taking medications, as performed by patients who are not bedridden.
- c. If an event is assessed as a "significant medical event," it must be reported as a serious adverse event, per the definition of serious adverse event in [Section 8.1.4](#).
- d. Grade 4 and 5 events must be reported as serious adverse events, per the definition of serious adverse event in [Section 8.1.4](#).

Reference source: Common Terminology Criteria for Adverse Events (CTCAE) version 5.0 published on November 27, 2017.

CTCAE severity grade will be presented in the AE listing. TEAEs by maximum severity will be summarized by SOC and PT for each treatment (active treatments, active treatment total, and pooled placebo) and overall.

#### **8.1.4. Serious Adverse Events**

Serious Adverse Events include adverse events that result in death, require either inpatient hospitalization or the prolongation of hospitalization, are life-threatening, result in a persistent or significant disability/incapacity, result in a congenital anomaly/birth defect, or are a significant medical event in the Investigator's judgement.

All serious TEAEs will be presented in a separate listing.

#### **8.1.5. Adverse Events Leading to Treatment Discontinuation**

The AEs where the answer to "Action Taken" on the AE eCRF is "Drug Withdrawn" will be identified in the AE listing.

#### **8.1.6. Adverse Events Leading to Death**

The AEs where the answer to "Outcome" on the AE eCRF is "Death" will be identified in the AE listing.

### **8.2. Clinical Laboratory Evaluations**

Clinical laboratory assessments will be performed by a central laboratory and collected according to the SOA (see [Appendix 14.1](#)).

For all numeric serum chemistry and hematology laboratory values, descriptive statistics for observed and change from baseline values will be presented for each laboratory test by scheduled visit and treatment (active treatments, active treatment total, and pooled placebo) and overall for the Safety Set. Listings will include all measured values.

All relevant clinical laboratory tests will be classified as Low, Normal, and High according to the normal ranges. This categorical data will be summarized in shift tables comparing the minimum post-baseline value, maximum post- baseline value, and the results at timepoint of interest post-baseline visit with those at the baseline visit. Shift table summaries will be

presented by treatment (active treatments, active treatment total, and pooled placebo) and overall for the Safety Set.

#### **8.2.4. Hematology**

The following hematology laboratory tests will be included:

- red blood cell (RBC) count
- mean corpuscular hemoglobin concentration (MCHC)
- mean corpuscular hemoglobin (MCH)
- mean corpuscular volume (MCV)
- red cell distribution width (RDW)
- hematocrit (Hct)
- hemoglobin (Hgb)
- white blood cell (WBC) count
- including differential count (neutrophils, eosinophils, basophils, lymphocytes, monocytes)
- platelet count

Summary tables will be presented as described in [Section 8.2](#) and data will be provided in a listing.

#### **8.2.5. Serum Chemistry**

The following serum chemistry laboratory tests will be included:

- bilirubin (total and conjugated)
- aspartate aminotransferase (AST)
- alanine aminotransferase (ALT)
- alkaline phosphatase (ALP)
- gamma glutamyl transferase (GGT)
- lactate dehydrogenase (LDH)
- creatine kinase (CK)
- protein
- albumin
- cholesterol (total, low density lipoprotein cholesterol (LDL-C))
- high density lipoprotein cholesterol (HDL-C)
- glucose
- blood urea nitrogen (BUN)
- creatinine
- sodium
- potassium
- chloride
- calcium
- magnesium
- C-reactive protein (CRP)

Summary tables will be presented as described in [Section 8.2](#) and data will be provided in a listing.

#### **8.2.6. Coagulation**

The following coagulation laboratory tests will be included:

- prothrombin time (PT)
- INR
- activated partial thromboplastin time (aPTT)

Since coagulation data are collected only at the screening visit, only a listing will be presented.

#### **8.2.7. Pregnancy Test**

Females of childbearing potential must have a negative urine or serum pregnancy test during screening. A urine or serum pregnancy test will also be performed on study days as mentioned in the schedule of assessments (SOA) (see [Appendix 14.1](#)).

A listing showing pregnancy test date and time, test result and reason for not doing pregnancy test (if not done) will be presented for the Safety Set.

### **8.3. Vital Sign Measurements**

Vital signs will be obtained after subject has been sitting for at least 1 minute and will include systolic blood pressure (mmHg), diastolic blood pressure (mmHg), heart rate (beats/minute), respiratory rate (breaths/minute), body temperature (C) and hemoglobin oxygen saturation (%) (via pulse oximetry).

Descriptive statistics for observed and change from baseline values will be presented for each vital sign test by scheduled visit and treatment (active treatments, active treatment total, and pooled placebo) and overall for the Safety Set.

Vital signs data will be presented in a listing for the Safety Set.

### **8.4. Physical Examination**

A complete physical examination will include an evaluation of the head, eyes, ears, nose and throat, and the cardiovascular, dermatologic, musculoskeletal, respiratory, gastrointestinal, and neurologic systems. Any abnormality identified at baseline (Screening Physical Exam) will be recorded as medical history.

A brief physical examination will focus on systems affected by AEs and at a minimum should include the cardiovascular and respiratory systems. Height and weight will be recorded at screening.

Changes from baseline abnormalities should be recorded in subject notes. New or worsened clinically significant abnormalities should be recorded as TEAEs. A categorical summary of physical examination results will be presented by scheduled visit and treatment (active treatments, active treatment total, and pooled placebo) and overall for the Safety Set.

Physical examination data will be presented in a listing for the Safety Set.

## 8.5. Electrocardiogram

A single standard 12-lead ECG will be performed at each scheduled visit. Lead placement should be as consistent as possible. ECG recordings must be performed after the subject has been resting in a supine position for at least 5 minutes.

ECG parameters to be evaluated include heart rate (HR) and the R to R interval (RR), Q to T (QT), P to R (PR) intervals and QRS duration. In addition, Fridericia's formula should be used to calculate the QT interval corrected for heart rate (QTcF). ECG morphology statements will also be evaluated with particular attention paid to waveform morphology findings of: ST segment abnormal, T wave changes, abnormal U waves, atrioventricular (AV) block, arrhythmia (supraventricular, ventricular, atrial fibrillation/flutter, etc.), and others including infarction, ischemia, and hypertrophy. ECG abnormalities will be recorded as AEs only if they are considered to be clinically significant by the Investigator.

Descriptive statistics for observed and change from baseline values will be presented for each ECG measurement by scheduled visit and treatment (active treatments, active treatment total, and pooled placebo) and overall for the Safety Set.

All ECG data will be listed with flags for QTcF values  $> 450$  msec and increase from baseline  $> 30$  msec.

## 8.6. Spirometry

Spirometry to assess forced expiratory volume 1 (FEV1), FVC, FEV1/FVC and the percent predicted for each of the parameters will be performed during Screening, Day 1, Day 7, Day 14, and Day 21. DLCO will be assessed only at Screening. Percent predicted will be calculated based on height, age, and ethnicity. Spirometry will be performed according to the current American Thoracic Society (ATS) / European Respiratory Society (ERS) Task Force guidelines (Miller et al., 2005). Spirometry will be performed on Days 1, 7, and 14 pre-dose and post-dose at 30 and 60 minutes (See Protocol section 7). Unscheduled spirometry may as be performed as needed for respiratory symptoms. If bronchospasm is suspected, spirometry may also be performed before and after a rescue beta-adrenergic agonist inhalation.

It is important to note that baseline values for spirometry are the mean of the Day 1 pre-dose and the value collected during screening using the same spirometry equipment. For example, if the initial spirometry for screening is done in a central spirometry laboratory, but Day 1 and subsequent spirometry is done with portable equipment in the clinic, then a second spirometry should be done in the screening period using the same portable equipment used in the clinic. The baseline value for each spirometry would thus be the mean of screening value using portable equipment and the Day 1 pre-dose value using portable equipment.

Descriptive statistics for observed and change from baseline values will be presented for each spirometry measurement by scheduled visit, timepoint, and treatment (active treatments, active treatment total, and pooled placebo) and overall for the Safety Set.

Line graphs of FEV1, FVC and 15% decrease from Baseline FEV1 will be presented by subject and visit for the Safety Set.

Spirometry data will be presented in a listing for the Safety Set.

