1.1.1.3 Clinical Background

LTI-03 was initially assessed in a Phase 1a study, LTI-03-1001: A Randomized, Double-Blind, Placebo-Controlled, Phase 1a, First-in-Man, Single Ascending Dose (SAD) and Multiple Ascending Dose (MAD) Safety, Tolerability and PK Study of a Cav-1-Scaffolding-Protein-Derived Peptide (LTI-03) in Healthy Adult Subjects. Twenty-four subjects were administered LTI-03 in 4 SAD cohorts at single doses of 10 mg, 40 mg, and 80 mg. At the 80 mg dose, subjects in 1 cohort were administered 4 20 mg capsules by inhalation and in a second cohort subjects at this 80 mg dose were administered 8 10 mg capsules by inhalation. Eight subjects in the combined SAD cohorts were administered placebo. In the SAD cohorts, 21 of the 24 subjects (88%) who were administered LTI-03 experienced treatment -emergent adverse events (TEAE), the most frequent of which were mild dry coughs that were considered to be related to LTI-03.

Twenty-nine subjects were administered LTI-03 by inhalation daily for up to 14 days in 5 MAD cohorts at doses of 2.5 mg once daily (QD), 5 mg QD, 5 mg twice daily (BID), 20 mg QD and 40 mg QD. The 2 higher dose MAD cohorts, 20 mg QD and 40 mg QD, were completed before the lower dose cohorts. The 3 lower doses were well tolerated. The most common TEAE in these 3 cohorts was a mild dry cough. During dosing in the 40 mg QD MAD cohort 1 subject developed severe TEAEs and two other subjects developed moderate TEAEs secondary to pulmonary airflow limitations (decreased forced expiratory volume 1 [FEV₁] and FEV₁/FVC ratios) that appeared to

be due to reversible airway obstruction. These events were considered to be dose limiting and related to LTI-03. There was no evidence that the TEAEs in the 3 subjects described previously were secondary to an allergic response. In the 20 mg QD MAD cohorts there were mild decreases in FEV₁ in two subjects that were not associated with TEAEs. These were not considered to be dose limiting. There were no serious adverse events (SAEs). All TEAEs were resolved 7 days after the treatment period. Further details can be found in the IB.

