5.6 Concomitant and Prohibited Medications

All medications (including over-the-counter medicines, herbal treatments, supplements, and vitamins) administered within 30 days of the Screening Visit through Study Day 21 will be recorded on the Case Report Form (CRF), using generic names when possible.

If the subject had participated in any clinical study before entering this study, then treatment with the investigational product must have been discontinued within 30 days or 5 half-lives (whichever is longer) prior to Screening.

Other anti-fibrotic therapies for the treatment of IPF are prohibited two months prior to the Baseline bronchoscopy until 1 week after the last dose of the study drug. If the investigator determines that anti-fibrotic therapy should be started before study completion, study drug should be discontinued, and early termination procedures completed as per Section 7.4.

N-acetyl cysteine or quercetin is prohibited within 7 days of dosing (Day 1) and throughout the Treatment Period.

Vaccines are prohibited within 2 weeks of dosing day (Day 1) and throughout the Treatment Period.

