6.7 Spirometry

Spirometry to assess FEV1, FVC, FEV1/FVC and the percent predicted for each of the parameters will be performed during Screening, Day 1, Day 7, Day 14, and Day 21. DLCO will be assessed only at Screening. Percent predicted will be calculated based on height, age, and ethnicity. Spirometry will be performed according to the current American Thoracic Society (ATS) / European Respiratory Society (ERS) Task Force guidelines (Miller et al., 2005). Spirometry will be performed on Days 1, 7, and 14 pre-dose and post-dose at 30 and 60 minutes. Unscheduled spirometry may as be performed as needed for respiratory symptoms. If bronchospasm is suspected, spirometry may also be performed before and after a rescue beta-adrenergic agonist inhalation.

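### SAP 8.6 has no rule for spirometry taken after a rescue bronchodilator and tabulates no unscheduled readings, so the spirometry tables can understate FEV1 falls

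*SAP*

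**What the plan says.** Protocol 6.7 and SAP 8.6 set the same schedule: "Spirometry will be performed on Days 1, 7, and 14 pre-dose and post-dose at 30 and 60 minutes". Both also allow tests outside it. The protocol's words are "Unscheduled spirometry may as be performed as needed for respiratory symptoms", and both documents add that "If bronchospasm is suspected, spirometry may also be performed before and after a rescue beta-adrenergic agonist inhalation".

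SAP 8.6 then defines three outputs:

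- **Summary table:** "Descriptive statistics for observed and change from baseline values will be presented for each spirometry measurement by scheduled visit, timepoint, and treatment", for the Safety Set.
- **Graphs:** "Line graphs of FEV1, FVC and 15% decrease from Baseline FEV1 will be presented by subject and visit for the Safety Set". The SAP does not say whether unscheduled readings are plotted.
- **Listing:** the spirometry data by subject.

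The section does not say how to treat a scheduled reading that follows a bronchodilator. It has no worst post-dose value and no count of subjects with a 15% fall in FEV1. The general rules in SAP 4 do not fill the gap.

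Other safety data get more. SAP 8.2 plans laboratory shift tables on minimum and maximum post-baseline values, and SAP 8.5 flags QTcF thresholds in the listing. Protocol 9.4.5.1 foresees, where appropriate, an incidence of normal-to-abnormal changes in its paragraph on ECG and spirometry. SAP 8.6 does not take this up.

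**The concern.** Spirometry is a named safety endpoint, and airflow limitation is the known toxicity. In the Phase 1a 40 mg once-daily cohort, Protocol 1.1.1.3 reports airflow limitation in three subjects that appeared to "be due to reversible airway obstruction. These events were considered to be dose limiting and related to LTI-03". The amendment history gives monitoring for airway obstruction as the reason for adding post-dose and as-needed tests.

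Consider a subject who wheezes 40 minutes after an observed dose. The unscheduled pre-rescue test shows the fall but belongs to no scheduled timepoint. The scheduled 60-minute test follows rescue and may look normal. The table then shows the recovery and not the fall.

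Rescue goes to subjects who obstruct. If obstruction is caused by the drug, as was judged in Phase 1a, the loss of information is greater on LTI-03 than on placebo and pulls the tabulated change toward no effect. With 9 active subjects per cohort, one masked case matters to a reader comparing the doses.

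**Working it through.** **1. The plan's own figure.** Protocol 9.5 and SAP 4.3 give the chance of seeing at least one event among 18 subjects on LTI-03 as 60% at a true rate of 5% and 85% at 10%. The formula is 1 − (1 − p)^n.

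- n = 18: 1 − 0.95^18 = 60.3%; 1 − 0.90^18 = 85.0%. Both reproduce.
- n = 9 (one dose cohort): 1 − 0.95^9 = 37.0%; 1 − 0.90^9 = 61.3%.

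These figures are not in dispute. They show that even a 10% event may appear once or not at all within a dose.

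**2. Where each reading goes under SAP 8.6 as written.**

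| Reading | Summary table | Line graph | Listing |
|---|---|---|---|
| Scheduled 30 or 60 min, before rescue | yes | yes | yes |
| Scheduled 30 or 60 min, after rescue | yes, unmarked | yes, unmarked | yes |
| Unscheduled, before rescue | no | not stated | yes |
| Unscheduled, after rescue | no | not stated | yes |

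**3. Illustration.** All FEV1 changes here are assumed, because the documents give none. Of 9 active subjects, k have a fall at an unscheduled pre-rescue test and then a post-rescue 60-minute value; the other 9 − k show 0% change. The mean is k × (change)/9.

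| | 60-minute row as planned (post-rescue −5% to +5%) | Worst post-dose value, unscheduled pre-rescue included (−15% to −30%) |
|---|---|---|
| k = 1, mean | −0.6% to +0.6% | −1.7% to −3.3% |
| k = 1, minimum | −5% to 0% | −15% to −30% |
| k = 1, fall ≥ 15% | 0/9 | 1/9 |
| k = 2, mean | −1.1% to +1.1% | −3.3% to −6.7% |
| k = 2, fall ≥ 15% | 0/9 | 2/9 |

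The median is 0% throughout, so it shows nothing in either column. For a single 20% fall fully reversed, the 60-minute mean differs from the one using the pre-rescue reading by 20/9 = 2.2 points. If rescue reverses half the fall, the difference is 10/9 = 1.1 points, and the −10% value still counts as 0/9. The comparison is with the pre-rescue reading; what an untreated 60-minute test would have shown is unknown.

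**4. Coverage.** Twice-daily dosing for 14 days without a second dose on Day 14 gives 14 × 2 − 1 = 27 planned doses. Scheduled post-dose tests follow three of them: 3/27 = 11%. A transient fall soon after a home dose could be caught only by an unscheduled test, which the table omits.

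**The case against.** The strongest reply is that the event would still be reported. Under Protocol 8.4.1 an abnormal test finding is an AE if it needs added drug treatment, comes with clinically significant symptoms, or leads to a change in dosing. A fall treated with rescue therefore belongs in the primary endpoint and the TEAE tables of SAP 8.1. If the criterion in Protocol 6.14.1 is met, study drug stops, and the case should also appear in the discontinuation count (SAP 8.1.1) and the disposition table (SAP 5.1). No hypothesis is tested, and the sponsor's medical officer and the CRO's medical monitor review safety continuously and before escalation. This stands, and it limits the point to the spirometry tables. It does not close the gap: those other tables carry no FEV1 magnitude, and Protocol 1.1.1.3 reports two subjects at 20 mg once daily with mild FEV1 decreases and no associated TEAE.

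A reader might also infer several stronger things that the documents do not support:

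- **That the planned tables as a whole hide airway obstruction.** The AE and disposition routes above contradict this. A fall already present at the 30-minute test before rescue would also show in that row and its minimum.
- **That unscheduled lows go only to a listing.** By-subject graphs are planned and may include them; the SAP is silent.
- **That the SAP directs post-rescue values to be treated as ordinary.** It gives no such direction; the result follows from the absence of a rule.
- **That the three Phase 1a subjects indicate a rate or size here.** The protocol gives no percentage fall and no rescue use for them. Their 40 mg once-daily dose was four times this trial's highest daily dose and eight times its highest single dose, and the lower-dose cohorts were well tolerated.
- **That bronchodilator use before visits is likely to distort readings.** Protocol 5.6 does not restrict bronchodilators, but asthma and significant obstructive disease are excluded and FEV1/FVC must be at least 0.7.
- **That Protocol 5.6, 6.7 and 6.14.1 conflict over which reading counts for discontinuation.** They do not contradict one another, so nothing needs reconciling there.

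**Conclusion.** The point holds for the spirometry summaries. Followed as written, SAP 8.6 lets a post-rescue value stand unmarked in a scheduled row and leaves an unscheduled pre-rescue nadir out of every spirometry summary table. Both can make falls look smaller and fewer, and the direction favours LTI-03 if obstruction is drug-related.

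On the assumed values, one fully reversed 20% fall among 9 subjects is worth 2.2 points on the 60-minute mean and the difference between 1/9 and 0/9 at the 15% level. This rests on rescue being given between the pre-rescue reading and the scheduled test, on the other subjects showing no change, and on the reversal assumed. How often that will happen at these doses is unknown. The change is a cheap improvement to the reporting of a safety endpoint; the primary endpoint does not depend on it.

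**What to change.** Amend SAP 8.6, analysis only:

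1. Flag each reading as pre- or post-bronchodilator from actual recorded times. Do not use times imputed under SAP 4.2: a missing start time on a dosing date is set to the dosing time, which would label the later readings after that dose as post-bronchodilator.
2. Present the scheduled summaries with and without post-bronchodilator values, and tabulate those values separately. Do not carry an earlier value forward. Tests around rescue are optional, so the last pre-rescue value may be the pre-dose one, and substituting it would erase a fall that was measured.
3. Add, by treatment, the worst post-dose change from baseline in FEV1 and FEV1/FVC, including unscheduled pre-rescue readings. Add the number of subjects whose readings meet the FEV1 and FEV1/FVC criterion already stated in Protocol 6.14.1.
4. Include unscheduled readings, marked as such, in the by-subject line graphs.

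The cost is one or two extra tables, linkage of spirometry to medication times, and slightly less favourable spirometry summaries. No procedure is added and no clinical rule is changed.
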